Investigational Medicinal Product(s), Dose, Dosage regimen, Treatment period, Formulation, Mode of Administration:	
The IMP will be supplied as weekly blister cards. All subjects will begin oral BID dosing with single-blind matching placebo on Visit 2 (Day –7) and continue through Visit 3 (baseline).
 
Trial assignments for the double-blind treatment period will be made once eligibility is confirmed. Eligible subjects will be randomized in a 1:1:1 ratio at baseline (Visit 3) to one of the following 3 treatment groups:
 
 • Centanafadine SR 200 mg • Centanafadine SR 400 mg • Matching placebo 
Subjects randomized to receive the target TDD of 200 mg centanafadine SR will start at the target dose on Day 1 of the double-blind treatment period and remain there for the duration of the trial. Subjects randomized to receive a TDD of 400 mg centanafadine SR will receive a TDD of 200 mg centanafadine SR on Day 1 of the double-blind treatment period for 7 days before they are escalated to their target TDD of 400 mg on Day 8 for the duration of the trial.
 
  
 Day(s)	Time	Total Daily Dose	
 
 200 mg Target	400 mg Target	
   
 1 through 7	2 tablets orally in morning	1 × 100 mg + 1 × PBO tablet	1 × 100 mg + 1 × PBO tablet	
 
 2 tablets orally 4-6 hr later	1 × 100 mg + 1 × PBO tablet	1 × 100 mg + 1 × PBO tablet	
 
 8 and thereafter	2 tablets orally in morning	1 × 100 mg + 1 × PBO tablet	2 × 100 mg	
 
 2 tablets orally 4-6 hr later	1 × 100 mg + 1 × PBO tablet	2 × 100 mg	
  
 
PBO = placebo.
 
Neither the investigator nor the subject will be aware of the treatment assignment after randomization. All doses of centanafadine SR and matching placebo should be taken orally BID and can be administered without regard to meals, and should be taken at approximately the same time each day, with the first dose taken in the morning. The second dose should be taken 4 to 6 hours after the morning dose is administered.
 
The total duration of the double-blind treatment period will be 6 weeks for all randomized subjects.
	Day(s)	Time	Total Daily Dose		200 mg Target	400 mg Target	1 through 7	2 tablets orally in morning	1 × 100 mg + 1 × PBO tablet	1 × 100 mg + 1 × PBO tablet	2 tablets orally 4-6 hr later	1 × 100 mg + 1 × PBO tablet	1 × 100 mg + 1 × PBO tablet	8 and thereafter	2 tablets orally in morning	1 × 100 mg + 1 × PBO tablet	2 × 100 mg	2 tablets orally 4-6 hr later	1 × 100 mg + 1 × PBO tablet	2 × 100 mg

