ordered from the largest to the smallest based on the number of evaluable subjects (ie, subjects who have baseline and at least 1 post-baseline value for the primary endpoint in the double-blind treatment period). The process will start by pooling the largest of the small centers with the smallest of the small centers until a non-small center is formed. This process will be repeated using the centers left out of the previous pass. In case of ties in center size, the center with the smallest center code will be selected. If any centers are left out at the end of this process, they will be pooled with the smallest pseudo centers, or if no pseudo centers exist, they will be pooled with the smallest non-small center.

In the case of gross violations of the linear model assumptions, nonparametric van Elteren test will be performed to compare the treatment effect at Day 42 in the double-blind treatment period on both last-observation-carried-forward (LOCF) and MI data. Details will be provided in the SAP.

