7.3.1.1.2 Sensitivity Analyses for Violation of Normality Assumption

The primary endpoint MMRM analysis is a maximum likelihood method that relies on the normality assumption. Residual analyses will be carried out to examine model assumption.

Protocol 405-201-00014

In the case of gross violations of the normality assumptions, nonparametric van Elteren test⁴⁷ will be performed to compare treatment effect at Day 42 on both LOCF dataset and MI data. The van Elteren test is a generalized Cochran Mantel Haenszel (CMH) procedure useful for stratified continuous data in non-normal setting. It belongs to a general family of Mantel-Haenszel mean score tests. The test is performed via SAS procedure PROC FREQ, by including CMH2 and SCORES=MODRIDIT options in the TABLE statement. The stratification factor is trial center.

In addition, other methods that are robust to distributional assumption will also be performed to provide different views on the primary efficacy result, these include generalized estimating equations (GEE), weighted GEE, and MI-robust regression.⁴⁸

For MI-van Elteren test and MI-robust regression, imputation datasets will be generated with SAS MI procedure, each dataset will be analyzed, and then an overall estimate is derived with SAS MIANALYZE procedure.

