In this hypothetical strategy, the event of withdrawing IMP is considered missing at random (MAR), and the primary endpoint of the trial could be considered as a combination of the responses of on-treatment completers at Day 42 and the imputation of the endpoint to Day 42 following the trend in each treatment group using the MMRM method for subjects who withdraw IMP during the trial. All data collected during the trial treatment period will be used for statistical analysis. For the primary efficacy analysis, the treatment effect will be estimated using the MMRM method described below. Under the MAR assumption, MMRM provides an unbiased estimate of treatment effect for the treatment period. Analyses with missing values imputed by multiple imputation under MNAR and other methods will be performed as sensitivity analyses. The primary analysis will be performed on Efficacy Sample which includes all randomized subjects who took at least 1 dose of IMP in the double-blind treatment period and who have both a baseline for the double-blind treatment period and at least one post-randomization AISRS total score during the double-blind treatment period. The primary efficacy analysis will be performed by fitting a MMRM analysis with an unstructured (UN) variance covariance structure in which the change from baseline for the double-blind

SAP 405-201-00014

treatment period in AISRS total score at the scheduled double-blind treatment period visits will be the dependent variable based on the OC data set. The model will include fixed class effect terms for treatment, study center, visit day, and an interaction term of treatment by visit day. The model will also include the interaction term of baseline values for the double-blind treatment period of AISRS Total score by visit day as covariates. The primary comparison between centanafadine (400 mg TDD group or 200 mg TDD group) and placebo at Day 42 in the double-blind treatment period will be estimated as the difference between Least Squares (LS) means utilizing the computing software SAS procedure PROC MIXED.

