8.1.3.4 Sensitivity Analyses for Violation of Normality Assumption

The primary endpoint MMRM analysis is a maximum likelihood method that relies on normality assumption. Residual analyses will be carried out to examine model assumption.

In the case of gross violations of the normality assumptions, nonparametric van Elteren test⁸ (van Elteren, 1960) will be performed to compare treatment effect at Week 14 on both LOCF dataset and Multiple Imputation (MI) data. The van Elteren test is a generalized CMH procedure useful for stratified continuous data in non-normal setting. It belongs to a general family of Mantel-Haenszel mean score tests. The test is performed via SAS procedure PROC FREQ, by including CMH2 and SCORES=MODRIDIT options in the TABLE statement. The stratification factor is trial center.

In addition, other methods that are robust to distributional assumption will also be performed to provide different views on the primary efficacy result, these include generalized estimating equations (GEE), weighted GEE (WGEE), and MI-robust regression⁹.

SAP 405-201-00014

For MI-van Elteren test and MI-robust regression, imputation datasets will be generated with SAS MI procedure, each dataset will be analyzed, then an overall estimate is derived with SAS MIANALYZE procedure.

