10.1 Study Visit Windows

Study visit windows will be used to map visits using study day intervals. This visit window convention applies to tables and listings for all efficacy and safety scales (AISRS, CGI-S, AIM-A, ASRS and CGI Change from Baseline). This derived study window variable will be named as DAY and will be footnoted. In listings it will be listed along with the eCRF study visit.

[Table 10-1](#) shows classifications for study day intervals in the double-blind treatment period. The variable “target day” is defined using the number of days since the start of double-blind dosing in the double-blind treatment period. The first day of double-blind dosing is defined as “Day 1”.

If more than one observation falls within a particular study day interval, then the last observation within that interval is used. Evaluations occurring more than three days after the last double-blind dosing date and evaluations occurring during the follow-up period will not be mapped into study visit windows and will be excluded from the double-blind treatment period analysis.

Table 10-1: Study Day and Visit Windows in the Double-Blind Treatment Period

Day	Target Day ^a	Study Day Interval ^a
-----	-------------------------	---------------------------------

SAP 405-201-00014

7	7	2-10
14	14	11-17
21	21	18-24
28	28	25-31
35	35	32-38
42	42	39-49 ^b

^a Relative to the first day of double-blind IMP in the double-blind treatment period.

^b Evaluations occurring more than three days after the last double-blind dosing date and evaluations occurring during the follow-up period will be excluded from the double-blind treatment period analyses.

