- CT-5.8.1 Summary of Mean Change from Baseline of the Double-Blind Treatment Period to the Double-Blind Treatment Period by Study Day in Adult ADHD Self Report Scale (ASRS) Scale - MMRM, UN (Efficacy Sample)
- CT-5.8.2 Summary of Mean Change Baseline of the Double-Blind Treatment Period to the Double-Blind Treatment Period by Study Day in Adult ADHD Self Report Scale (ASRS) Scale - LOCF (Efficacy Sample)
- CT-5.8.3 Summary of Mean Change from Baseline of the Double-Blind Treatment Period to the Double-Blind Treatment Period by Study Day in Adult ADHD Self Report Scale (ASRS) Scale - OC (Efficacy Sample)
- CT-5.8.4 Summary of Mean Change from Baseline to End of Single-Blind Placebo Run-in Period in Adult ADHD Self Report Scale (ASRS) Scale - OC (Efficacy Sample)
- CT-5.9.1 Summary of Mean Change from Baseline of the Double-Blind Treatment Period to the Double-Blind Treatment Period by Study Day in ASRS Inattentive Subscale - MMRM, UN (Efficacy Sample)
- CT-5.9.2 Summary of Mean Change Baseline of the Double-Blind Treatment Period to the Double-Blind Treatment Period by Study Day in ASRS Inattentive Subscale - LOCF (Efficacy Sample)
- CT-5.9.3 Summary of Mean Change from Baseline of the Double-Blind Treatment Period to the Double-Blind Treatment Period by Study Day in ASRS Inattentive Subscale - OC (Efficacy Sample)
- CT-5.9.4 Summary of Mean Change from Baseline to End of Single-Blind Placebo Run-in Period in ASRS Inattentive Subscale - OC (Efficacy Sample)
- CT-5.9.5 Summary of Mean Change from Baseline of the Double-Blind Treatment Period to the Double-Blind Treatment Period by Study Day in ASRS Hyperactive-Impulsive Subscale - MMRM, UN (Efficacy Sample)

SAP 405-201-00014

- CT-5.9.6 Summary of Mean Change Baseline of the Double-Blind Treatment Period to the Double-Blind Treatment Period by Study Day in ASRS Hyperactive-Impulsive Subscale - LOCF (Efficacy Sample)
- CT-5.9.7 Summary of Mean Change from Baseline of the Double-Blind Treatment Period to the Double-Blind Treatment Period by Study Day in ASRS Hyperactive-Impulsive Subscale - OC (Efficacy Sample)
- CT-5.9.8 Summary of Mean Change from Baseline to End of Single-Blind Placebo Run-in Period in ASRS Hyperactive-Impulsive Subscale - OC (Efficacy Sample)
- CT-5.10.1 Summary of Mean Change from Baseline of the Double-Blind Treatment Period to the Double-Blind Treatment Period by Study Day in Adult ADHD Investigator Symptom Rating Scale (AISRS) Total Score – MI, VAN ELTEREN TEST (Efficacy Sample)

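### SAP 8.1.3.4 sets the conditional van Elteren test at Week 14 of a trial whose endpoint is Day 42, and does not say that each dose is compared with placebo

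*SAP*

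**What the plan says.** SAP 8.1.3.4 provides that, if residual checks show gross departures from normality, a van Elteren test will "compare treatment effect at Week 14 on both LOCF dataset and Multiple Imputation (MI) data". It is to be run in PROC FREQ "by including CMH2 and SCORES=MODRIDIT options in the TABLE statement", with trial center as the stratum. The MI version is to be combined through PROC MIANALYZE. No pair of arms is named.

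The protocol places the same test elsewhere in time. Section 7.3.1 says a "nonparametric van Elteren test will be performed to compare the treatment effect at Day 42 in the double-blind treatment period", and section 7.3.1.1.2 has it "compare treatment effect at Day 42 on both LOCF dataset and MI data". The protocol names no pair of arms either.

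The rest of the plan is consistent about timing. The protocol synopsis states: "The total duration of the double-blind treatment period will be 6 weeks for all randomized subjects". SAP 8.1 defines the primary endpoint at Day 42. In SAP 10.1 the last analysis window, labelled Day 42, covers study days 39 to 49, and the text adds: "Evaluations occurring more than three days after the last double-blind dosing date and evaluations occurring during the follow-up period will not be mapped" into those windows. On contrasts, SAP 8.1.1 speaks of "The primary comparison between centanafadine (400 mg TDD group or 200 mg TDD group) and placebo at Day 42", and the fixed sequence in SAP 8.2 also goes dose by dose.

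**The concern.** There are two problems. First, read literally, the rule points to a time with no AISRS value to test. The label could also be misread as Day 14, which is a scheduled visit. Second, the rule does not say what is compared. An omnibus test asks whether the three arms differ anywhere; the trial asks whether each dose beats placebo.

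What is at stake is the rank-based fallback for the primary endpoint. If a reader doubts normality, this test is what the plan offers, so its time point and contrasts should be fixed in advance. They should not be left for the analyst to settle when several visits and more than one test form are available.

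**Working it through.** **1. The plan's own figures.** With 135 per arm, a difference of 5 and an SD of 12.5 (SAP section 4):

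- 5 / (12.5 × √(2/135)) = 3.286
- 3.286 − 1.960 = 1.326, and Φ(1.326) = 0.908, which agrees with the stated power of at least 90%
- 405 / 0.90 = 450 randomized, as stated

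Neither figure involves the van Elteren test, so neither changes.

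**2. The time point.**

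| Item | Source | Study day |
|---|---|---|
| Primary endpoint | SAP 8.1 | 42 (week 6) |
| End of last analysis window | SAP 10.1, Table 10-1 | 49 (week 7) |
| Latest scheduled AISRS, widest allowances | Protocol Tables 3.7-1 and 3.7-2 | 42 + 2 + 7 + 2 = 53 |
| Week 14 | SAP 8.1.3.4 | 14 × 7 = 98 |

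Differences: 98 − 42 = 56 days, 98 − 49 = 49 days, 98 − 53 = 45 days. The Day 53 figure assumes that the last dose falls on the day of the Day 42 visit. Counting from consent does not help, since the synopsis gives total participation as 12 to 13 weeks.

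**3. Carrying forward does not help.** SAP 5.2 builds the LOCF data set only at scheduled double-blind visits, so there is no Week 14 record to fill. The same holds for imputation, because Day 42 is the last visit in the analysis.

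**4. Degrees of freedom.** A stratified mean-score test has (arms − 1) degrees of freedom: 3 − 1 = 2 if all arms enter, and 2 − 1 = 1 if the data are restricted to one dose and placebo. The CMH2 and modified-ridit options do not restrict the arms.

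The related output STAT-4.8 shows what a three-arm layout gives. At Day 42 its row-mean-score statistic is 10.7158 on 2 df. For 2 df the chi-square tail is exp(−x/2), so exp(−5.3579) = 0.0047, as printed. The 1-df line beside it (2.7238, p = 0.0989) is a correlation across all three arms in coded order, not a dose-versus-placebo contrast. STAT-4.8 uses rank scores and LOCF data only. It is a valid supplementary output, but it is not the test specified in 8.1.3.4 and gives no result for either dose.

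**5. Pooling.** PROC MIANALYZE combines an estimate with its standard error. A 2-df omnibus chi-square supplies neither as a single quantity, so the MI version also points to a two-arm form.

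The pairwise rank results cannot be computed here, because the documents contain no subject-level data.

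**The case against.** The strongest reply is that this is a one-word slip with only one sensible reading. The protocol says Day 42 twice and the SAP's endpoint is Day 42. Planned table CT-5.10.1 in SAP 13 is laid out by study day within the double-blind period. STAT-4.8 covers Days 7 to 42, so nothing suggests anyone worked to Week 14. This stands as to consequence. A reader might infer that the test cannot be performed or was aimed at the wrong visit; the documents do not support that. It does not make the sentence in the signed SAP correct.

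On contrasts, the source cited for the test is, by its title, about two-sample Wilcoxon tests. The primary comparisons are already dose against placebo, and the SAP does not restate contrasts for GEE, weighted GEE or MI-robust regression either. This stands in part: pairwise is the natural reading. However, 8.1.3.4 describes the test as a generalized CMH procedure, gives options that accept three arms, and the related rank output was run on three.

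Three stronger readings go beyond the documents:

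- *The LOCF version was dropped*, because SAP 13 names only an MI van Elteren table. That list is headed as proposed and names no MI-robust regression table either, and SAP 8.1.4 and 8.5 send some outputs to separate statistical documentation.
- *The trigger was met*, because Shapiro-Wilk gives p < 0.0001 in all 12 residual tests in STAT-6.1.1. The W values are 0.962 to 0.979 and Day 42 skewness is −0.47. The plan does not define a gross violation, and the documents record no judgment.
- *The specified test was never run.* The CT outputs are not in the documents, so this cannot be known.

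**Conclusion.** The point holds and is minor. Week 14 is wrong by 56 days against the endpoint, contradicts the protocol in two places, and should read Day 42. Separately, the section names no contrast, and its options applied to three arms give a 2-df omnibus result that does not match the primary comparisons.

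Nothing confirmatory depends on this: the primary MMRM, the fixed sequence, alpha and power are unchanged. Dose-specific LOCF ANCOVA results are also available in STAT-4.2 (p = 0.0016 for 200 mg and 0.0011 for 400 mg versus placebo), and other robust methods are planned in the same section.

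The conclusion assumes that the sensitivity test is meant to mirror the primary comparisons at the primary time point. The protocol states the time point. The contrasts are inferred from SAP 8.1.1 and 8.2.

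**What to change.** - In SAP 8.1.3.4, read Day 42 for Week 14.
- Specify two separate two-arm van Elteren tests of 1 df each, 400 mg versus placebo and 200 mg versus placebo, with modified ridit scores, stratified by pooled center as formed under SAP 10.2.

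The SAP was signed on 26 May 2020, the analysis data set is dated 16 June 2020 and the statistical outputs 31 August 2020. The change should therefore be a dated erratum or a note in the report. The note should separate the two parts: Day 42 restores what the protocol already specified, while the two-arm form clarifies a contrast left unstated.

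The cost is one word and one sentence. If the test is reported, it also needs a short run on existing data. No new data are required.

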8.1.4 Subgroup Analyses

Subgroup analyses of change from baseline of the double-blind treatment period in AISRS total score to every scheduled visit in the double-blind treatment period will be performed by the following factors:

- Sex (Based on the biological status)
- Race (White and All Other Races)

All subgroup analyses will be conducted using the same MMRM analysis as for the primary efficacy analysis except that the fixed class effect term for trial center will not be included in the model.

Interaction effects of treatment-by-subgroup will be assessed at Day 42 for the subgroups identified in the previous paragraph. MMRM analyses will be performed by adding addition of terms for subgroup-by-day and treatment-by-subgroup-by-day. These treatment-by-subgroup interaction analyses will be presented in statistical documentation.

8.2 Key Secondary Efficacy Endpoint

The key secondary efficacy endpoint is the change from baseline of the double-blind treatment period to Day 42 using the CGI-S. This key secondary efficacy endpoint will be analyzed by fitting the same MMRM model described in the primary analysis.

To control the overall experiment-wise type I error at 0.05 level, A fixed sequence testing approach will be applied. The statistical test will be performed in the following order:

- 1) Change from baseline to Day 42 in the double-blind treatment period in AISRS total score between centanafadine 400 mg TDD and placebo;
- 2) Change from baseline to Day 42 in the double-blind treatment period in AISRS total score between centanafadine 200 mg TDD and placebo;
- 3) Change from baseline to Day 42 in CGI-S score between centanafadine 400 mg TDD and placebo;
- 4) Change from baseline to Day 42 in CGI-S score between centanafadine 200 mg TDD and placebo.

The testing procedure will stop at the first comparison where the p-value is ≥ 0.05 . None of the subsequent comparisons will be performed.

SAP 405-201-00014

8.3 Other Efficacy Endpoints

Other efficacy analyses are listed below. All other efficacy variables will be evaluated at a nominal 0.05 level (2-sided) without adjusting for multiplicity.

- 1) Change from baseline in AISRS total score for every scheduled visit during the double-blind treatment period other than the Day 42 visit;
- 2) Change from baseline for the Inattentive subscale and Hyperactive-Impulsive subscale of the AISRS for scheduled visits during the double-blind treatment period, separately at every visit
- 3) Change from baseline in CGI-S for every scheduled visit during the double-blind treatment period other than the Day 42 visit
- 4) CGI Change from Baseline will be collected at each scheduled visit
- 5) Percentage of responders at each post-baseline visit during the double-blind treatment period, where a responder is defined as a subject with a CGI Change from Baseline score of 1 or 2 OR a $\geq 30\%$ improvement in ADHD symptoms compared with baseline as measured by the AISRS total score
- 6) Response rate at each post-baseline visit during the double-blind treatment period, where response is defined as
 - a) a CGI Change from Baseline score of 1 or 2 OR a $\geq 20\%$ improvement in ADHD symptoms compared with baseline as measured by the AISRS total score.
 - b) a CGI Change from Baseline score of 1 or 2 OR a $\geq 40\%$ improvement in ADHD symptoms compared with baseline as measured by the AISRS total score.
- 7) Remission rate for every scheduled visit during the double-blind treatment period, where remission is defined as AISRS total score ≤ 18 .

Variable (1) through variable (3) will be evaluated using the same MMRM model described in the primary analysis. Variable (4) will be evaluated by the Cochran Mantel Haenszel (CMH) Row Mean Score Differ Test controlling, in LOCF analysis, for trial center. Variable (5) through variable (7) will be evaluated by the CMH General Association Test controlling, in LOCF analysis, for study center. An OC analysis will also be conducted for variables (4) through (7) but will not control for trial center. Separate summary and statistical test for response rate based only on the AISRS improvement and only on the CGI Change from Baseline score will be presented for (5) and (6).

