3.2.2 Double-blind Treatment Period

Trial assignments for the double-blind treatment period will be made once eligibility is confirmed. Eligible subjects will be randomized in a 1:1:1 ratio at baseline (Visit 3) to one of the following 3 treatment groups:

- Centanafadine SR 200 mg TDD
- Centanafadine SR 400 mg TDD
- Matching placebo

Neither the investigator nor the subject will be aware of the treatment assignment after randomization. All doses of centanafadine SR and matching placebo should be taken orally BID and can be administered without regard to meals, and should be taken at approximately the same time each day, with the first dose taken in the morning. The second dose should be taken 4 to 6 hours after the morning dose is administered.

Subjects randomized to receive the target TDD of 200 mg centanafadine SR will start at the target dose on Day 1 of the double-blind treatment period and remain at that dose for the duration of the trial (Table 3.2.2-1). Subjects randomized to receive a TDD of 400 mg centanafadine SR will receive a TDD of 200 mg centanafadine SR on Day 1 of the double-blind treatment period for 7 days before they are escalated to their target TDD of 400 mg on Day 8 for the duration of the trial (Table 3.2.2-1).

Protocol 405-201-00014

Table 3.2.2-1 Dosing Schedule for Centanafadine SR Tablets			
Day(s)	Time	Total Daily Dose	
		200 mg Target	400 mg Target
1 through 7	2 tablets orally in morning	1 × 100 mg + 1 × PBO tablet	1 × 100 mg + 1 × PBO tablet
	2 tablets orally 4-6 hr later	1 × 100 mg + 1 × PBO tablet	1 × 100 mg + 1 × PBO tablet
8 and thereafter	2 tablets orally in morning	1 × 100 mg + 1 × PBO tablet	2 × 100 mg
	2 tablets orally 4-6 hr later	1 × 100 mg + 1 × PBO tablet	2 × 100 mg

PBO = placebo.

For subjects randomized to placebo, they will take 2 placebo tablets in the morning and 2 tablets in the afternoon for the duration of treatment.

Once the subject is at the target dose, further dose modification is not permitted. Dose modification is not allowed at any time during the trial.

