5.2 Handling of Missing Data

The mixed-effect model repeated measure (MMRM) assumes data are missing at random (MAR), which is a reasonable assumption in longitudinal clinical trials in MDD¹. However, the possibility of “missing not at random” (MNAR) data can never be ruled out. As sensitivity analyses, selection model², pattern-mixture model^{3,4,5,6}, and/or shared parameter model⁷ will be used to explore data missing mechanisms of MNAR and investigate the response profile of dropout patients by last dropout reason under MNAR mechanism for the following 3 scenarios: 1) Dropout reasons due to either AE or LOE as MNAR, 2) Dropout reasons due to either AE or LOE or subject withdrew consent as MNAR, 3) All dropouts as MNAR using

SAP 405-201-00014

both 1) Delta adjustment imputation method which is to departure from MAR assumption by progressively increasing the delta until conclusion from the primary analysis is overturned, and 2) Placebo based imputation methods in which missing data for both placebo and drug group are imputed based on the imputation model derived from placebo data. If drug improved outcomes prior to dropout, this benefit is carried into subsequent imputed values, but will diminish over time in accordance with the correlation structure. Details are provided in [Section 8.1.3 Sensitivity Analysis](#). The observed-cases (OC) data set will consist of actual observations recorded at each visit during the double-blind treatment period and no missing data will be imputed. MMRM, Wu-Bailey, and pattern-mixture model will be performed on the OC dataset.

The last-observation-carried-forward (LOCF) data set will include data recorded at a scheduled double-blind treatment period visit or, if no observation is recorded at that visit, data carried forward from the previous scheduled double-blind treatment period visit. Baseline data (e.g., the last visit of the single-blind placebo run-in period) will not be carried forward to impute missing values for the LOCF data set. The analysis of covariance (ANCOVA) analysis will be performed for the change from baseline to the end of the double-blind treatment period (Day 42, LOCF) in AISRS total score as sensitivity analysis. The ANCOVA_LOCF model includes treatment and study center as main effects, and baseline value as a covariate.

ANCOVA analysis with OC data will also be conducted on change from baseline for AISRS total score, as well as all continuous change from baseline efficacy endpoints.

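### CGI-Change, response and remission have no missing-at-random analysis, although AISRS and CGI-S do, and the remission test leaves out a strongly prognostic baseline score

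*SAP*

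**What the plan says.** SAP 8.3 gives AISRS, its subscales and CGI-S the primary MMRM. CGI-Change gets a CMH row-mean-scores test on LOCF data, stratified by center. For the 30% responder rate, the 20% and 40% response rates and remission, "Variable (5) through variable (7) will be evaluated by the CMH General Association Test controlling, in LOCF analysis, for study center". The alternative is stated next: "An OC analysis will also be conducted for variables (4) through (7) but will not control for trial center". None of these tests has a baseline term.

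SAP 5.2 defines LOCF: "if no observation is recorded at that visit, data carried forward from the previous scheduled double-blind treatment period visit". Baseline is not carried. Protocol 7.3.2.2 has the same LOCF-CMH and observed-case scheme for CGI-Change and the 30% responder rate; remission and the other response cut-offs appear only in the SAP.

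Remission is an AISRS total of 18 or less, in subjects who must score at least 28 at baseline (Protocol 3.4.2). Under Protocol 3.2.2 the 400 mg arm takes 200 mg "for 7 days before they are escalated to their target TDD of 400 mg on Day 8".

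SAP 8.1.1 targets the primary AISRS effect had nobody withdrawn, with withdrawal treated as MAR. For SAP 8.3, "All other efficacy variables will be evaluated at a nominal 0.05 level (2-sided) without adjusting for multiplicity".

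**The concern.** Response and remission are the rates that clinicians are likely to read first. Two separate features affect them.

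1. **Missing data.** The plan regards MAR as reasonable and uses it for AISRS and CGI-S, but no planned analysis of CGI-Change, response or remission is MAR-based. LOCF fixes a dropout at the last rating. If dropout differs by arm, so does the distortion. In the 400 mg arm an early dropout's carried score may also predate the target dose.

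2. **Baseline, for remission only.** A subject entering at 28 needs a 10-point fall to reach 18; one entering at 50 needs 32. CGI-Change and the response rules are already relative to baseline, so this point does not extend to them.

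**Working it through.** **Inputs.** Observed-case counts: STAT-4.7. LOCF counts: STAT-4.6. MMRM estimates: STAT-4.1.1 and STAT-5.1. LOCF estimates: STAT-4.2 and STAT-5.2. Baseline moments: STAT-4.2. Baseline sum of squares and error variance: STAT-4.3.

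**Check on the counts.** AISRS observed-case counts for Days 7, 14, 21, 28, 35 and 42:

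- 200 mg: 137, 132, 127, 122, 115, 113
- 400 mg: 139, 125, 116, 114, 104, 102
- placebo: 139, 132, 132, 130, 125, 123

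Visit totals are 415 + 389 + 375 + 366 + 344 + 338 = 2227, exactly the number of observations in the printed MMRM.

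**Carried at Day 42 (LOCF count minus observed count).**

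- 400 mg: 140 − 102 = 38 (27.1%)
- 200 mg: 140 − 113 = 27 (19.3%)
- placebo: 141 − 123 = 18 (12.8%)

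**Ratings from the Day 7 window.** At Day 14 the 400 mg arm has 140 LOCF and 125 observed scores, so 15 are carried from Day 7. A subject whose last score lies in the Day 7 window has no Day 14 score and must be among these 15, so 15 is a ceiling at Day 42. The floor is 0, because the counts do not show who returned later. The window covers study days 2 to 10 (SAP 10.1). A scheduled Visit 4 rating precedes the first 400 mg dose, because the new card is started the day after the visit (Protocol 3.7.1.4.1). An early-termination rating on Days 8 to 10 might not.

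**Effect at Day 42 against placebo, MMRM to LOCF.**

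| Scale | Dose | MMRM | LOCF | Shrinkage |
|---|---|---|---|---|
| AISRS | 400 mg | −4.42 | −4.05 | 0.37/4.42 = 8% |
| AISRS | 200 mg | −4.01 | −3.88 | 0.13/4.01 = 3% |
| CGI-S | 400 mg | −0.282 | −0.236 | 0.046/0.282 = 16% |
| CGI-S | 200 mg | −0.329 | −0.301 | 0.028/0.329 = 8% |

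The 400 mg shifts are 0.37/1.32 = 0.28 and 0.046/0.125 = 0.37 of the MMRM standard error. CGI-S is the nearest printed proxy for CGI-Change.

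**Baseline and remission (LOCF scale, normal model assumed).** Within-arm baseline sum of squares = 139 × 6.750² + 139 × 6.956² + 140 × 6.348² ≈ 18,700. Slope of change on baseline = −√(618.37/18,700) = −0.182; this returns the printed adjusted means −10.782, −10.918 and −7.199. Remission = Φ((18 − m)/s), with m the mean Day 42 score and s = √(0.818² × SD² + 110.58).

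- Placebo: m = 37.65 − 7.13 = 30.51, s = 11.73, giving 14.3%.
- 400 mg at its own baseline: m = 38.76 − 11.06 = 27.71, s = 11.96, giving 20.8%.
- 400 mg at the placebo baseline: m = 27.71 − 0.818 × 1.12 = 26.79, giving 23.1%.
- 200 mg: 22.7% at its own baseline, 22.6% at placebo's.

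The 400 mg difference is about 6.5 points unadjusted and 8.8 adjusted, so imbalance costs about 2.3 points. The 200 mg difference stays at 8.3 to 8.4. In the 400 mg arm the model gives remission of 47% at baseline 28, 19% at 38 and 4% at 50.

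**Validity and precision.** A simulated center-stratified CMH without baseline, using the 39 reported center sizes (10,000 runs, assumed center SD 3), rejected a true null 5.0% of the time. Adjusting the risk difference for baseline by logistic standardization cut its variance: unadjusted over adjusted was 1.08 on the LOCF scale (140 per arm) and 1.11 with MMRM parameters (135 per arm), 2,000 trials each.

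**The case against.** The strongest case is that little depends on this. These endpoints are nominal and outside the fixed sequence, the AISRS conclusion is the same under LOCF (p = 0.0011) as under MMRM (p = 0.0009), and LOCF works against the drug. The SAP states the hypothetical estimand for the primary endpoint, and Protocol 7.3.2.1 extends it to CGI-S, but neither assigns it to these variables. An observed-case analysis is also planned. All of this stands and limits the weight of the point. Observed cases, however, drop center as well as carried scores, so the two analyses differ in two ways at once. The printed Day 42 observed-case ANCOVA (STAT-4.3) also has 421 observations and the LOCF raw means, where STAT-4.7 counts 338; whether the CMH tables share this is not shown.

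A reader might also infer more than the documents support:

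- **That 15 of 140 Day 42 results at 400 mg are 200 mg scores.** Only a range of 0 to 15 follows. Dropout was not strictly monotone: the 400 mg LOCF count rises from 139 at Day 7 to 140 at Day 14. The count is for AISRS; no CGI-Change counts are printed, and CGI-S has 2220 observations against 2227. Nor do the 15 look like early failures: their mean change is (−1136 + 1011)/15 = −8.3, against −8.1 for observed Day 14 scores.
- **That the missing baseline term causes the carry-forward problem.** It does not; adding baseline would leave every carried score in place.
- **That remission is confounded with baseline.** Arms are randomized and the test keeps its size. The imbalance is compatible with chance (1.12 points, p = 0.16), works against 400 mg and is nil for 200 mg.
- **That about 11 points of remission benefit are at issue.** That figure comes from MMRM means; the planned LOCF scale gives about 6.5 to 7 unadjusted.

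Finally, logistic regression with center dummies would be fragile: 11 of the 39 pooled centers hold only 3 to 5 subjects, and at an assumed 20% remission about 8 centers would have no remitter.

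**Conclusion.** The concern holds as two limited points. CGI-Change, response and remission lack the MAR analysis that the plan gives to AISRS and CGI-S, while carried scores differ by arm (27%, 19%, 13%) and LOCF pulls the 400 mg effect down more than the 200 mg effect, by under 0.4 standard errors. For remission alone, omitting baseline AISRS gives up roughly 8 to 11% in variance and leaves about 2 points of chance imbalance uncorrected at 400 mg.

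The carried-score counts are exact for AISRS and assumed similar for CGI-Change. The remission figures rest on a normal model, although the printed residual tests reject normality (STAT-6.1.1), so they indicate size only. The change is worth making but affects no confirmatory conclusion.

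**What to change.** Add a MAR-based analysis. Take the standard MAR imputations already specified as a step in SAP 8.1.3.1, add CGI-Change to the imputation model, and derive each response definition and remission from the completed data. Compare each dose with placebo with baseline AISRS as a covariate (required for remission) and report risk differences. Handle center without separation, for example by conditional or penalized logistic regression, or by standardization without center dummies. Keep LOCF-CMH and observed cases as supportive, and confirm that the observed-case tables really exclude carried scores.

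Protocol 7.3.2.2 should be aligned. Because outputs already exist, the alternative is to label the new analysis supplementary.

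The cost is SAP wording, modest programming and more modelling for nominal endpoints. The listed imputation tables cover AISRS and CGI-S, so CGI-Change is genuinely new work.
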